5.6. Detailed description of study procedures

The sections that follow provide an overview of the procedures that are to be followed in enrolling, evaluating, and following subjects who participate in this clinical study. An outline is provided in [Table 5](#). An overview of the data collected during the course of the study is given in Section [5.6.1](#).

During special circumstances, exemplified by the COVID-19 pandemic, certain study procedures may be adapted to protect the subject and promote data integrity. Refer to Section [5.6.15](#) for further details.

5.6.1. Data collected from subjects

The following data will be collected from each subject over the duration of their study participation:

- Demographic information
- Medical history
- Vaccination history
- Prior and concomitant medication, as defined in Section [6.7](#).
- Pre-vaccination body temperature
- 30 minutes post-vaccination immediate reactions: signs or symptoms of anaphylaxis, allergic phenomena (such as rashes, itching, or other allergic manifestations).
Solicited Local (**administration site**) and systemic data (including e.g., use of medication to treat or prevent fever and/or pain, body temperature measurement).

- Adverse Events (AEs):
 - Post-vaccination solicited local (**administration site**) and systemic AEs (including related information such as use of medication to treat or prevent fever), collected at home by subjects' parent(s)/LAR(s), and recorded on Subject eDiary for 7 days following each vaccination visit (including the day of vaccination) or until they resolve or Day 30 (whichever occurs first). Specific systemic AEs (parotid/salivary gland swelling, fever and rash) will be collected for 30 days (including the day of vaccination) following the MMR and VV vaccinations at Visit 5.
 - Unsolicited AEs occurring within 30 days after each vaccination will be collected by interviewing the subject's parent(s)/legal guardian(s) and by review of available medical records at the next visit.
 - SAEs will be collected from study Day 1 until study end, inclusive.
 - Medically attended AEs (including any medical visit) will be collected from study Day 1 until study end, inclusive.
 - AEs leading to premature withdrawal from the study will be collected from study Day 1 until study end, inclusive.
 - AESIs (pIMDs, seizures, and arthritis) will be collected from study Day 1 until study end, inclusive.

All data collected must only be identified using the GSK Subject ID, as described in Section 5.2.

5.6.2. Pre-vaccination procedures (Visit 1)

A pre-vaccination clinic visit may occur within 5 days prior and up to the time of the vaccination Visit 1 on Day 1 (inclusive). The following procedures will be performed for each potential subject prior to the first vaccination at Visit 1:

- Obtaining informed consent from subject's parent(s)/LAR(s).
- Subject ID assignment
- Screening the subject for eligibility based in the inclusion and exclusion criteria listed in Section 4. This includes all the following procedures: collecting demography and medical history, review of systems, collecting prior and concomitant medications (including vaccination history), and general physical examination by a qualified health care practitioner
- Subject enrolment.
- Subject randomization.

If a pre-vaccination clinic visit was performed, the investigator will review and confirm subject eligibility on Day 1 (Visit 1) prior to first vaccination. Unless deemed necessary, procedures performed during pre-vaccination clinic visit should not be repeated on Day 1 (Visit 1). If a pre-vaccination clinic visit did not occur, all procedures mentioned here will be performed at Visit 1 instead.

5.6.3. Informed consent

The signed/witnessed/thumb printed informed consent of the subject's parent(s)/LAR(s) must be obtained before study participation. Refer to Section [5.1](#) for the requirements on how to obtain informed consent as appropriate.

5.6.4. Check inclusion and exclusion criteria

Check all inclusion and exclusion criteria as described in Sections [4.2](#) and [4.3](#) after obtaining informed consent and before randomization.

5.6.5. Collect demographic data

At Visit 1, record demographic data such as date of birth, gender, race and ethnic origin, weight and length in the subject's eCRF.

Collection of sex, race and ethnicity data is necessary to assess and monitor the diversity of the trial participants, and to determine if the trial participants are truly representative of the impacted population.

5.6.6. Medical history

Obtain the subject's medical history by interview and/or review of the subject's medical records and record any pre-existing conditions or signs and/or symptoms present in a subject prior to the first study vaccination in the eCRF.

Medical history will be collected at Visit 1 (or pre-visit 1, if applicable), including but not limited to any medical history that may be relevant to subject eligibility for study participation such as prior vaccinations, concomitant medications (refer to Section [5.6.13](#)), and previous and ongoing illnesses or injuries. Relevant medical history can also include any medical history that contributes to the understanding of an AE that occurs during study participation, if it represents an exacerbation of an underlying disease/pre-existing problem.

Review of systems is a structured interview that queries the subjects' parent(s)/legal guardian(s) as to any complaints the subject has experienced across each organ system. This will be performed before enrolment and used to guide physical examination. A general physical examination is to be performed by a qualified health care professional. "Qualified health care professional" refers to any licensed or certified health care professional who is permitted by institutional policy to perform physical examinations and who is identified within the Study Staff Signature Log. The physical examination will include a check of general appearance, the measurement of vital signs (rectal body temperature preferable [as subjects are <12 months of age], and heart rate), auscultation of heart and lungs, measurement of length and weight. The medical history-directed exam of other body parts and systems to assess eligibility will be performed during Visit 1.

5.6.7. Physical examination

At Visits 2 through 7, a brief symptom-directed physical examination is to be performed if necessary according to symptoms the subject's parent(s)/LAR(s) has reported. This is a physical examination that will include an examination of organ systems that are relevant to the investigator based only on review of the subject's reported adverse events and concomitant medication use. This assessment may include measurement of heart rate and temperature.

These data will be written in the source document. Should the physical assessment reveal any abnormal values or events, these must be documented in the eCRF Adverse Events Form.

Treatment of any abnormality observed during this examination should be performed according to local medical practice outside this study or by referral to an appropriate health care provider.

5.6.8. Check contraindications, warnings and precautions to vaccination

Contraindications, warnings and precautions to vaccination must be checked at the beginning of each vaccination visit. Refer to Sections [6.5](#) and [6.6](#) for more details.

5.6.9. Assess pre-vaccination body temperature

The body temperature of each subject needs to be measured prior to any study vaccines administration. If the subject has fever [fever is defined as a body temperature $\geq 38.0^{\circ}\text{C}/100.4^{\circ}\text{F}$ regardless the location of measurement on the day of vaccination], the vaccination visit will be rescheduled within the allowed interval for this visit (see [Table 6](#) and Section [6.5](#)).

5.6.10. Study group and treatment number allocation

Study group and treatment number allocation will be performed as described in Section [5.2.2](#). The number of each administered treatment must be recorded in the eCRF.

5.6.11. Sampling

The following clinical specimen is required to be collected from each subject in this study:

- Blood samples for serologic evaluation.

Refer to the Module on Biospecimen Management in the SPM and the Central Laboratory Investigator Manual for detailed instructions for the collection, handling and processing of the samples.

5.6.11.1. Blood sampling for immune response assessments

Blood samples will be obtained from each enrolled subject in both study groups at 3 study visits as follows:

- Visit 4 at Day 151, i.e., 30 (-9 to +30) days after the 3rd vaccination.
- Visit 5 at Day 301, i.e., 180 (-7 to +91) days after the 3rd vaccination (pre-4th vaccination).
- Visit 6 at Day 331 i.e., 30 (-9 to +30) days after the 4th vaccination.

In order to support all serological assay testing, a volume of approximately 5 mL of whole blood (to provide approximately 2 mL of serum) should be drawn from each subject at each pre-defined timepoint mentioned above, resulting in a total of approximately 15 mL over the entire study period. After centrifugation, serum samples should be kept at -20°C/ -4°F or below until shipment. Refer to the SPM and Central Laboratory Investigator Manual for more details on sample storage conditions.

A topical anesthetic (e.g. EMLA adhesives or cream) may be used at the site of blood sample draw, according to local practice, in order to minimize pain.

The blood will be used for immunological assays, as described in Section [5.7.4](#).

In clinic visits where a blood draw and a vaccination are planned, ensure all serology samples are taken **prior** to vaccination. The following are clinical circumstances that warrant delay of blood samples collection for immunogenicity assessments in this study:

- Receipt of systemic antibiotics within the previous 3 days (72 hours) before blood sample collection

In the event that a subject meets the criterion for delay of blood samples collection, blood samples collection may proceed once the appropriate window for delay has passed.

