2. OBJECTIVES AND ENDPOINTS

Objectives	Endpoints

 To assess the safety and tolerability of rMenB+OMV NZ, PCV13 and other RIV when administered concomitantly to healthy infants at 2, 4, 6 and 12 months of age, throughout the study duration. 	
 The percentages of subjects with solicited local Adverse events (AEs) (administration site event) and systemic AEs during the 7 days (including the day of vaccination) after the 1st, the 2nd, the 3rd and the 4th vaccination (Visits 1, 2, 3 and 5). The percentages of subjects with solicited systemic AEs of parotid/salivary gland swelling, fever and rash during the 30 days (including the day of vaccination) after the 4th vaccination (Visit 5). The percentages of subjects with all unsolicited AEs (including SAEs, AEs leading to withdrawal, AESIs, and medically attended AEs) during 30 days (including the day of vaccination) after the 1st, the 2nd, the 3rd and the 4th vaccination (Visits 1, 2, 3 and 5). The percentages of subjects with SAEs, AEs leading to withdrawal, AESIs and medically attended AEs from study Day 1 (Visit 1) until study end (6 months or 12 months after last study vaccination, Visit 7*).

 To demonstrate the sufficiency of the immune response to rMenB+OMV NZ when administered concomitantly with PCV13 and other RIV to healthy infants at 2, 4 and 6 months of age, at one month after the 3rd vaccination. 
Criteria: The sufficiency of the immune response to rMenB+OMV NZ at one month after the 3rd vaccination will be demonstrated if the adjusted lower confidence limit for the percentage of subjects achieving serum bactericidal assay using human complement (hSBA) titers \geq Lower Limit of Quantitation (LLOQ) is \geq 60% for the N. meningitidis serogroup B test strains M14459, 96217, NZ98/254, M13520 (individually); and is \geq 50% for all strains combined (composite endpoint).
	
 At 1 month after the 3rd vaccination (Day 151): 
 the percentages of subjects with hSBA titers \geqLLOQ; for each of the M14459, 96217, NZ98/254 and M13520 test strains. the percentages of subjects with hSBA titers \geqLLOQ for all strains combined (composite endpoint).

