5.6.13. Post-vaccination procedures

The following post-vaccination procedures for each subject will be performed on Day 1 (Visit 1), Day 61 (Visit 2), Day 121 (Visit 3), and Day 301 (Visit 5). After vaccination, the subject will be observed for at least 30 minutes including observation for solicited and unsolicited AEs, including measurement of body temperature. Record all safety data collected during this time in the subject's source document and eCRF.

The site should schedule the next study activity clinic visit or safety follow-up call with the subject's parent(s)/LAR(s). The subject's parent(s)/LAR(s) should be reminded of the next planned study activity. Instruction regarding recording of safety data will be provided by the site based on the visit script

In addition, the post-vaccination procedures related to the reporting of solicited AEs will be performed on Day 1 (Visit 1), Day 61 (Visit 2), Day 121 (Visit 3), and Day 301 (Visit 5). The eDiary will be dispensed at Day 1 (Visit1) to subjects and the subject's parent/LAR will bring the eDiary at each clinic visit. The eDiary will be collected by site staff at Day 151 (Visit 4). A new eDiary will be provided to the subjects again at Day 301 (Visit 5) and collected by the site staff at Day 331(Visit 6). A script will be provided to site staff monitoring safety to advise the subjects parent(s)/LAR(s) on collecting and reporting of solicited safety data.

At each vaccination visit, the vaccine injection sites(s) will be stored in the eDiary.

The eDiary is the only source for collection of solicited local (*administration site*) and systemic AEs starting after the initial 30 minutes post-vaccination; therefore, **it is critical that the subject's parent(s)/LAR(s) complete the Subject Diary correctly**. The subject's parent(s)/LAR(s) will be instructed on how and when to complete each field of the Subject Diary (see Section [5.6.16.1](#)).

The subject's parent(s)/LAR(s) should be instructed how to perform body temperature measurement (preferably rectal for subjects <12 months of age and the axilla for subjects \geq 12 months of age) using the thermometer provided by the site. If the subject is unusually hot or cold during the day, the subject's parent(s)/LAR(s) should check body temperature. If the subject has fever, the highest body temperature observed that day

should be recorded in the eDiary. Temperature measurements should be taken prior to the administration of any antipyretic medication.

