5.6.14.1. Follow-up safety clinic visit

Follow-up clinic visits will be performed in the clinic on Day 151 (Visit 4) and on Day 331 (Visit 6).

The subject's parent(s)/legal guardian(s) will be interviewed to determine if any unsolicited AEs occurred and if any concomitant medications or vaccines were taken/received in the time since the last clinic visit. The qualified healthcare professional reviewing these data will discuss the symptoms (if any) reported by the subject and will determine if any additional diagnoses and/or AEs are present. Adverse events reported by the subject's parent(s)/LAR(s) at this follow-up clinic visit must be recorded in the subject's source document and on an Adverse Events eCRF, as specified Section [7](#).

A symptom-directed physical examination will be performed if necessary according to symptoms reported by the subject's parent(s)/LAR(s). This is a physical examination that will include an examination of organ systems that are relevant to the investigator based on review of the subject's reported AEs, concomitant medication use. This assessment may include: vital signs (at a minimum body temperature [rectal for subjects <12 months of age and axilla for subjects ≥ 12 months of age, preferably] and a check of general appearance. The physical assessment must be performed by the investigator or designee of the investigator, who is qualified to perform a physical assessment in accordance with their institutional policy (see [glossary of terms](#) for definition of a qualified healthcare provider). Any relevant clinical finding resulting from the symptom-directed physical examination should be documented in the subject's source document and eCRF(s).

At both visits on Day 151 (Visit 4) and Day 331 (Visit 6), the eDiary should be returned to the study site; *the eDiary dispensed at Day 1 (Visit1) will be collected at Day 151 (Visit 4) and the eDiary dispensed at Day 301 (Visit 5) will be collected at Day 331 (Visit 6)*. For details on the eDiary see Section [5.6.16.1](#). A blood sample will also be collected for immunological evaluation at both visits.

The site should schedule the next study activity with the subject's parent(s)/LAR(s). The subject's parent(s)/LAR(s) will receive a written reminder of the next planned study activity. Instruction regarding recording of safety data will be provided by the site based on the visit script.

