5.6.16.1. Subject Diary

A electronic Diary (eDiary) hereafter referred to as Subject Diary will be used in this study to capture solicited adverse events. The subject's parent/LAR should be trained on how and when to complete each field of the Subject Diary.

Subject Diary training should be directed at the individual(s) who will perform the measurements of adverse events and who will enter the information into the Subject Diary. This individual may not be the subject's parent/LAR, but if a person other than the subject's parent/LAR enters information into the Subject Diary, this person's identity must be documented in the subject's source record. Any individual that makes entries into the Subject Diary must receive training on completion of the Subject Diary at the time of the visit when Subject Diary is dispensed. This training must be documented in the subject's source record.

The same individual should preferably complete the Subject Diary throughout the course of the study.

The subject's parent(s)/LAR(s) should be trained on how to self-measure local solicited adverse events and body temperature.

The measurement of solicited local AEs (**administration site event**) is to be performed using the ruler provided by the site.

Subject's parent(s)/LAR(s) will be instructed to measure and record the rectal (subjects <12 months of age) or axillary (subjects ≥12 months of age) body temperature in the evening. Should additional temperature measurements be performed at other times of day, subject's parent(s)/LAR(s) will be instructed to record the highest temperature in the Subject Diary.”

Subject Diary assignment and use (at Visit 1 and Visit 5):

- Each subject's parent/LAR will be assigned a Subject Diary and shown how to use the device – this will include how to access the diary, performing test data entry on sample questions, and how to charge and store the device.
- The subject's parent/LAR will self-select a numeric access code secret to themselves. The same individual should preferably make the assessments and complete the Subject Diary throughout the relevant reporting period.
- The subject's parent(s)/LAR(s) will select an alarm time that suits their daily routines whilst ensuring compliance with protocol requirements.

Subject Diary instructions must ensure that the subject's parent(s)/LAR(s) understands the following:

- Timely completion of the Subject Diary on a daily basis is a critical component to study participation.

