5.6.16.1.1. Subject diary alerts

The subject's parent(s)/LAR(s) will receive daily reminders via the Subject Diary device's in-built audio-visual alarms to alert the user to complete the diary during the post vaccination period, which is from Day 1 to Day 7 after Visits 1, 2 and 3 (or until the solicited AE resolves) and from Day 1 to Day 30 after Visit 5.

The Subject Diary system will also allow for regular alerts to be issued via email to site staff indicating where subjects may need to be contacted due to:

- Non-compliance (i.e. failing to enter or transmit diary data),
- Reporting of any severe solicited reactions,
- Subject experienced any AE that required hospitalization or visit to the emergency room or medically attended events that were of concern to the parents/LAR(s).

Sites must assess these alerts when received and contact subjects as necessary. Please refer to Section 8.2 on the premature withdrawals from the study and Section 7.2.3 on the evaluation of AEs for guidance on necessary action in the event of one of these alerts.

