**4.1.2. Exposed Set**

All subjects in the Enrolled Set who receive a study vaccination.

**4.1.3. Safety Set****4.1.3.1. Solicited Safety Set (solicited local and systemic adverse events and other solicited adverse events)**

All subjects in the Exposed Set with any solicited adverse event data.

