**4.1.5. Per Protocol (PP) Set for Immunogenicity**

All subjects in the FAS Immunogenicity who:

- Correctly receive the vaccine (i.e., receive the vaccine to which the subjects are randomized and at the scheduled time points).
- Have no protocol deviations leading to exclusion in at least one timepoint of analyses for immunogenicity.
- Are not excluded due to other reasons defined prior to unblinding or analysis.

Examples for subjects excluded due to other reasons than protocol deviations are:

- Subjects who withdrew informed consent.

Examples for subjects excluded due to protocol deviations are:

- Subjects who did not receive all the study vaccines up to Dose 3 for primary 3 doses analyses or up to Dose 4 for the 4th dose analyses.
- who received a vaccine not specified or forbidden in the protocol up to Visit 4 for primary 3 doses or up to Visit 6 for the 4th dose.

- who received a medication/product leading to exclusion from a per-protocol analysis as listed in Protocol Section 6.7.2 up to Visit 4 for primary 3 doses or up to Visit 6 for the 4th dose.
- who presented a medical condition leading to exclusion from a per-protocol analysis as listed in Protocol Section 6.8 up to Visit 4 for primary 3 doses or up to Visit 6 for the 4th dose.
- who did not comply with the post Dose 3 (for primary 3 doses) or pre and post Dose 4 (for the 4th dose) blood sample schedule, i.e. 21 to 60 days post the vaccination.
- who had no immunogenicity results post Dose 3 (for primary 3 doses) or post Dose 4 (for the 4th dose).

The allowed intervals between each study visit are given in [Table 5](#). Subjects will not be eligible for inclusion in the per-protocol cohort for analysis of primary 3 doses if study visits are performed outside this interval up to visit 4, and they will not be eligible for analysis of the 4th dose if the study visit is performed outside this interval up to Visit 6.

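### An in-window Visit 6 at 21 to 29 days after dose 4 takes back the eDiary before Day 30, so the 30-day rash, parotid swelling and fever percentages can be slightly low

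*Protocol*

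**What the plan says.** **Visit timing.** Protocol 5.6.11.1 gives the last sample as "Visit 6 at Day 331 i.e., 30 (-9 to +30) days after the 4th vaccination". Protocol Table 6 and SAP Table 5 state the same window as 21 to 60 days between Visits 5 and 6, and SAP 4.1.5 repeats it for the per-protocol set: "blood sample schedule, i.e. 21 to 60 days post the vaccination".

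**Endpoint.** Protocol section 2 lists among the primary safety endpoints the percentages with "parotid/salivary gland swelling, fever and rash during the 30 days (including the day of vaccination") after dose 4. SAP 5.4.1.1 splits this period at Day 7, so the later interval is Day 8 to Day 30.

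**Diary.** Protocol 5.6.13 states: "The eDiary is the only source for collection of solicited local" and systemic events once the 30-minute observation is over. Protocol 5.6.14.1 says "the eDiary dispensed at Day 301 (Visit 5) will be collected at Day 331 (Visit 6"). The reminder alarms in Protocol 5.6.16.1.1 are set to run "from Day 1 to Day 30 after Visit 5". Parents are told in Protocol 5.6.16.1 to measure "body temperature in the evening".

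**Denominator.** The Solicited Safety Set (SAP 4.1.3.1) is "All subjects in the Exposed Set with any solicited adverse event data". The missing-data rule in Protocol 9.3 is triggered by the share of subjects with no solicited data at all in an interval.

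**The concern.** The protocol asks for 30 days of diary data after dose 4, but allows the device to be returned from Day 22 onward without any deviation. An infant seen that early cannot supply the last days of the window.

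Neither the analysis-set definition nor the 20% rule recognises a partly observed interval. The SAP has rules for implausible values, duplicates and several entries on one day, but none for a diary that ends early by schedule.

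If such an infant has no recorded event by the time of hand-in, the natural reading of a simple percentage puts the infant in the denominator with no event. At stake is the accuracy of within-group percentages for a named primary safety endpoint: rash, parotid swelling and fever, which the protocol follows to Day 30 because of the MMR and varicella vaccines.

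**Working it through.** **Inputs from the documents.** Optimal interval 30 days, window -9 to +30 (Protocol 5.6.11.1). Endpoint of 30 days, with the vaccination day as Day 1 (Protocol section 2). Later interval Day 8 to Day 30, which is 30 - 7 = 23 days (SAP 5.4.1.1). Diary returned at Visit 6 (Protocol 5.6.13 and 5.6.14.1).

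**The plan's own figure.** 30 - 9 = 21 and 30 + 30 = 60, which reproduces the 21 to 60 days in Protocol Table 6.

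**Days lost per infant.** A visit d days after dose 4 falls on diary Day d + 1. Days lost are 30 - d if the visit-day entry was not made before hand-in, and 29 - d if it was.

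| d (days after dose 4) | Diary day | Lost, no visit-day entry | Lost, with visit-day entry |
|---|---|---|---|
| 21 | 22 | 9 | 8 |
| 25 | 26 | 5 | 4 |
| 29 | 30 | 1 | 0 |
| 30 or more | 31 or later | 0 | 0 |

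For fever the third column is the likelier one, because temperature is taken in the evening. The largest loss is 9/30 = 30% of the full window, or 9/23 = 39% of Day 8-30. At a Day 22 visit, Days 8 to 21 (14 of 23 days) are still observed, so the infant has data in the interval and does not count towards the 20% rule. The compliance measure in SAP 5.4.2.9 divides by 30, so this infant could reach at most 21/30 = 70% (22/30 = 73% with the visit-day entry).

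**Effect on the percentage.** Let f be the share of infants seen at 21 to 29 days and q the share of first onsets that fall on the lost days. If unobserved days count as event-free, the relative understatement is f × q, which lies between 0 and f. The documents give neither f nor q.

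**Illustration, with assumed inputs.** Take f = 5% to 30%, early visits spread evenly over Day 22 to 30 (mean loss 5 days, or 4 with the visit-day entry) and uniform onset.

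- 30-day window: 5% × 4/30 = 0.67% to 30% × 5/30 = 5.0% relative.
- Day 8-30: 5% × 4/23 = 0.87% to 30% × 5/23 = 6.5% relative.
- At an assumed observed 30-day percentage of 20%: 20/(1 - 0.0067) - 20 = 0.13 points, to 20/(1 - 0.05) - 20 = 1.05 points.

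For scale, the 95% Clopper-Pearson interval at 20% is 17.3 to 22.9 for 160/800 (half-width 2.8 points) and 16.2 to 24.3 for 80/400 (half-width 4.0 points). The shift is below both, and would be smaller if onset is mostly early.

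**The case against.** **The effect is small and the same in both arms.** This stands. The optimal interval is 30 days, the window extends much further late than early, the endpoints are descriptive, and even the assumed upper value is inside the confidence interval. But an equal schedule does not restore a within-group percentage, and the share of infants seen early is not planned to be reported.

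**Late events are not lost.** Partly true. Under Protocol 10.2, a reaction told to the site instead of entered in the diary goes on the AE page as unsolicited, and SAP 5.4.2.4 has a table combining solicited and unsolicited events. Such an event still does not enter the solicited percentage that the endpoint names. The compliance tables in SAP 5.4.2.9 would show short diaries but would not correct the percentage.

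**Unseen documents may cover it.** The table shells are in the OPS (SAP section 9), and the study procedures manual is also not available. Counting lost days as event-free is therefore an inference from the SAP text, not a stated rule. Table 5 of the protocol may mark 30-day diary recording beyond Visit 6, but its layout is damaged in the available text, and the wording of 5.6.13 and 5.6.14.1 is explicit about return at Visit 6.

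**A stronger reading that does not hold.** DTPa and Hib are given at Visit 6, so a reader might infer that the Day 1-30 unsolicited, SAE, AESI and medically attended summaries are contaminated for infants seen early. The documents do not support calling that an error:

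- The endpoint counts all events in 30 days whatever their cause (Protocol section 2 and 7.2.1).
- Other vaccines are foreseen at Visit 6 as well (Protocol 6.1.2).
- Protocol 7.1.1 makes clear that footnote 3 of Table 3 means only that no study-specific assessment of the non-study vaccines is planned. It does not stop collection after dose 4.
- Attribution is handled by the causality assessment (Protocol 7.2.3.2.2) and the separate summary of related events (SAP 5.4.1.1).

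**Conclusion.** The point holds and is minor. Visits that comply fully with the protocol can remove 1 to 9 of the 30 diary days (0 to 8 if the visit-day entry was made), with no rule for the shortened interval. The 30-day and Day 8-30 percentages for rash, parotid swelling and fever can then be slightly low within each arm. The Day 1-7 solicited tables are unaffected.

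The day counts follow from the documents. The size of the bias does not: 0.1 to 1.1 percentage points at an observed 20% depends on assumed values for the share seen early, even spacing of early visits and uniform onset, and on lost days being counted as event-free. A reader should not infer a built-in difference between arms or any threat to a success criterion; the documents support neither.

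**What to change.** **Conduct, only if any infant is still to have Visit 6.** Schedule the visit at least 30 days after dose 4, within the existing 21 to 60 day window, or leave the eDiary with the family until Day 30. With a visit at 30 days or later, no diary day is lost. The SAP is dated June 2025 and the documents do not say whether any such visits remain.

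**Analysis, SAP 5.4.1.1.** Keep the main tables as defined and add:

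1. The number of infants per arm with Visit 6 less than 30 days after dose 4.
2. A repeat of the 30-day and Day 8-30 percentages for rash, parotid swelling and fever, either in infants with Visit 6 at 30 days or later, or as a cumulative incidence censored at the last diary day.

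The first option in item 2 selects on visit date and not on diary completeness. Restricting to infants whose entries reach Day 30 would be a poor substitute, because whether a family keeps entering data may depend on symptoms. The censored version keeps all infants but assumes that the end of diary entry is unrelated to later events.

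**Cost.** A few lines of SAP text and one or two descriptive tables from visit dates and diary data already collected. The restricted repeat has a smaller denominator, so it should be read beside the main table and not in place of it.
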